### **Oxygen Saturation**

Results for oxygen saturation as collected on the “Oxygen Saturation” eCRF page will be listed.

## **15.5 Other Safety or Tolerability Evaluations**

### **ECG**

Single 12-lead ECGs will be obtained as outlined in the protocol using an ECG machine that automatically calculates the heart rate and measures PR, QRS, QT, and QTc Intervals. ECG parameters will be derived from the data collected on the “Electrocardiogram” eCRF page. Shift table for ECG interpretation value at baseline and value at end of treatment will be provided.

A listing of ECG values will be provided including participant identifier, age, sex, race, ECG parameter and unit, visit, ECG date, value, change from baseline. Baseline values and post-baseline values collected after the on-treatment period will be flagged. Qualitative ECG results will also be provided in the listing.

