M7824 has shown promising clinical efficacy signal in BTC patients progressing after platinum-based 1L treatment (Study MS200647-0008). Thirty Asian participants were treated with M7824 at dose of 1200 mg every 2 weeks. As of 20 March 2018, 30 participants who had previously received 1L treatment for BTC, received M7824 for a median duration of 8.9 weeks (range: 2 to 57.6 weeks); 5 participants remained on treatment at the time of data cutoff. Seven participants had a confirmed objective response (OR) by Investigator read (ORR 23.3%) and 6 participants had a confirmed OR by IRC (ORR 20%), including 1 confirmation of response after cutoff. Per anatomical location, the ORR was 14.3% (1 out of 7) in study participants with extrahepatic CCA and 40% (4 out of 10) in study participants with intrahepatic CCA, 16.6% (2 out of 12) in study participants with gallbladder carcinoma. No responses were observed in ampullary cancer (0 out of 1). With a minimum follow-up of 8 months, the duration of response (DOR) ranged from 0.7 to 6.9 months with 5 of 7 responses ongoing at the data cutoff date. Besides the confirmed ORR, 1 additional participant had an ongoing partial response (PR) for 7.6+ months after initial progression. The observed clinical efficacy, therefore, compares favorably to the calculated benchmark of existing 2L treatment options and there is a strong rationale with preclinical and clinical data to justify further clinical development of M7824 in 2L BTC, with the potential to establish M7824 as the standard of care.

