## Physical Examination (Including Vital Signs and 12-Lead ECGs)

Physical examination findings, including vital signs (body temperature, respiratory rate, heart rate, and blood pressure) and 12-lead ECGs, as indicated in the Schedule of Activities (Table 1) will be presented.

Further details will be provided in the IAP based on current safety experience applying the latest MedDRA version.

All safety analyses will be performed on the Safety Analysis population.

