### **Abnormal Laboratory Findings and Other Abnormal Investigational Findings**

Abnormal laboratory findings and other abnormal investigational findings (e.g., on an ECG trace) should not be reported as AEs unless they are associated with clinical signs and symptoms, lead to study intervention discontinuation or are considered otherwise medically important by the Investigator. If a laboratory abnormality fulfills these criteria, the identified medical condition (e.g., anemia or increased ALT) must be reported as the AE rather than the abnormal value itself.

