### Definition of on-treatment period:

On-treatment period is defined as the time from the first study intervention to the last study intervention date + 30 days OR the earliest date of subsequent anticancer therapy minus 1 day, whichever occurs first, unless otherwise stated. For participants with treatment ongoing at cut-off date, all data from the first study intervention up to the cut-off date will be considered under the on-treatment period.

For immune-related AEs as listed in Section 15.2.4.2, an expanded on-treatment period will be used as a default for any analysis:

Time from the first study intervention to the last study intervention date + 90 days, death OR to the earliest date of subsequent anticancer therapy minus 1 day, whichever occurs first, unless otherwise stated.

Any systemic anticancer therapy, any anticancer surgery and any anticancer radiotherapy as documented in the "Anti-cancer treatment after discontinuation" CRF page will be considered as subsequent anticancer therapy.

The on-treatment period will include the initial treatment period as well as the reinitiation of treatment period, as applicable. Whether a participant reinitiates treatment (following the rules as outlined in the protocol) or not, the on-treatment period is defined as the time from the first study intervention administration to the last study intervention administration date + 30 days or the earliest date of subsequent anticancer drug (anticancer therapy, anticancer surgery and anticancer radiotherapy) therapy minus 1 day, whichever occurs first, unless otherwise stated.

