### Unscheduled assessments:

As per database definition, the safety unscheduled assessments are always linked to a scheduled timepoint (each unscheduled assessment is linked to the previous scheduled timepoint). Safety data retrieved from an unscheduled timepoint (vital signs, electrocardiogram [ECG] and laboratory data) will be analyzed according to the following scenario:

- For shift table, they will be taken into account in the definition of the worst assessment during study
- For description at each timepoint post-baseline, the first available result (in chronological order) per timepoint will be taken into account in the analysis in case of multiple values
- For description at baseline, the last available result before first study intervention will be taken into account in the analysis in case of multiple values

For immunogenicity analysis, unscheduled visits will also be taken into account in the analysis following the same rules as detailed above.

For PK analysis, unscheduled samples will not be linked to a scheduled timepoint and will be excluded from summaries.

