### 10.1 Disposition of Participants and Discontinuations

Descriptive statistics will be used to summarize participant disposition based on the electronic case report form (eCRF) data.

The following information will be reported:

- Total number of participants screened (i.e. participants who gave informed consent)
- Number of participants who discontinued from the study prior to study intervention overall and grouped by the main reason (e.g. the failed specific inclusion or exclusion criteria, adverse event, lost to follow-up, death, progressive disease, withdrawal of consent and other)

- Number of re-screened participants
- Number of participants who received at least one dose of study intervention (ITT/SAF analysis set)
- Number of participants with treatment ongoing at the data cutoff date
- Number of participants off study treatment, grouped by main reason (treatment completed as per protocol, progressive disease, death, adverse event, lost to follow-up, protocol non-compliance, withdrew consent, other)
- Number of participants who re-initiated the study treatment and number of participants who discontinued the study intervention after re-initiation
- Number of participants with treatment ongoing
- Number of participants who completed/discontinued the study participation, with the associated main primary reason (study completed according to protocol, adverse event, lost to follow-up, protocol non-compliance, death, withdrew consent, other)

Percentages will be calculated based on the number of participants in the ITT/SAF population, except for the number of screened and re-screened participants where no percentage will be provided.

In addition, the number of participants in each analysis set defined in Section 8.2 will be summarized, overall and by region (Europe, North America, Asia), country within region and center.

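### The only ECG table in the SAP compares baseline with end of treatment, so abnormalities on 28-day and unscheduled ECGs are listed but not counted unless reported as adverse events

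*SAP*

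**What the plan says.** SAP Section 15.5 (ECG) specifies one tabulation: "Shift table for ECG interpretation value at baseline and value at end of treatment will be provided". Everything else is a listing, by visit and date, of ECG values, change from baseline and qualitative results, with values collected after the on-treatment period flagged.

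Protocol Table 1 places the 12-lead ECG at Screening, at the End-of-Treatment visit and at the 28-day Safety Follow-up visit. None is scheduled during the treatment phase.

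SAP Section 9 (Unscheduled assessments) includes ECG in its scope: "Safety data retrieved from an unscheduled timepoint (vital signs, electrocardiogram [ECG] and laboratory data) will be analyzed according to the following scenario". Its rule for shift tables is: "For shift table, they will be taken into account in the definition of the worst assessment during study". For descriptions at a post-baseline timepoint, it uses the first available result linked to that timepoint, and each unscheduled assessment is linked to the scheduled timepoint before it.

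Protocol Section 9.4.2 sets a modest requirement: "12-lead ECGs, as indicated in the Schedule of Activities (Table 1) will be presented".

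**The concern.** A baseline to end-of-treatment shift describes one post-baseline moment. An ECG prompted by symptoms or by suspected cardiac toxicity during treatment, or the scheduled ECG about four weeks after the last dose, can be abnormal without altering that table. Section 9 appears to anticipate this by bringing unscheduled values in through a worst assessment, but the ECG table defines no worst assessment for the rule to act on.

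Myocarditis is among the important identified risks named in Protocol Sections 2.3 and 6.9.2, so a reader of the study report may want a count of participants whose ECG became abnormal at any time on treatment. As planned, that count would have to be built by hand from the listing.

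**Working it through.** There is no planned figure to reproduce. The check sets the relevant texts side by side.

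**1. Scheduled ECGs and the table.** Post-baseline ECG visits in Protocol Table 1: End-of-Treatment and 28-day follow-up, so 2. Visits used by the Section 15.5 table, reading end of treatment as that visit: 1. The 28-day ECG is left to the listing.

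**2. Can unscheduled ECGs enter through Section 9?** There are two post-baseline routes.
- *Shift-table route.* Unscheduled values count towards the worst assessment. The ECG table has a baseline value and an end-of-treatment value only, so it contains no worst assessment.
- *By-timepoint route.* An ECG taken during treatment links back to an earlier timepoint, not forward to the End-of-Treatment visit. One taken after the End-of-Treatment ECG links to that visit but is not the first result there. It could enter only if the scheduled End-of-Treatment ECG was missing.

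**3. Comparable tables in the same SAP.**

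| Output | Compared with baseline |
|---|---|
| Gradable laboratory parameters (SAP 15.3) | Highest on-treatment grade |
| Non-gradable laboratory parameters (SAP 15.3) | Highest and lowest on-treatment values |
| ECOG performance status (SAP 15.5) | Highest on-treatment score |
| ECG interpretation (SAP 15.5) | Value at end of treatment |

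ECG is the only one of these without a worst on-treatment value, and no reason is given.

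**4. Which 28-day ECGs would a worst on-treatment column include?** The visit window is 28 ± 5 days after the last dose: 28 − 5 = 23 and 28 + 5 = 33. The on-treatment period in SAP Section 9 ends at last dose + 30 days, or the day before subsequent anticancer therapy if that is earlier. ECGs on days 23 to 30 therefore count as on-treatment when no new therapy has started, and those on days 31 to 33 do not. The actual visit dates are unknown, so no proportion is claimed.

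**5. What reaches other tables?** Protocol Appendix 4 states that "other abnormal investigational findings (e.g., on an ECG trace) should not be reported as AEs unless they are associated with clinical signs and symptoms". It adds two further triggers: discontinuation of study intervention, or the investigator's judgement of medical importance. ECG changes meeting any of the three are adverse events and reach the TEAE tables if treatment-emergent. Protocol Table A9 treats an abnormal ECG in suspected immune cardiac toxicity as Grade 1, with drug held and corticosteroids considered. SAP Section 15.2.4.2 can flag such an event as immune-related if its preferred term and the other criteria are met. What is left without a count is mainly asymptomatic ECG change not reported as an adverse event.

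**The case against.** The strongest reply is that a shift to the scheduled End-of-Treatment ECG is a legitimate descriptive choice. The protocol asks only that ECGs be presented, the listing shows the values and qualitative results by visit, and clinically relevant changes are captured as adverse events. All of that stands, and it is why the point is small.

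The reply also says that Section 9 gives rules by type of output and does not promise every output for every data type. Vital signs are named in the same sentence as ECG, yet SAP Section 15.4 plans no vital-sign shift table. That is a fair answer to anyone who infers a direct contradiction. Section 9 signals the use of worst values; it does not by itself require an ECG table built on them. It is less complete as an answer for ECG, because here a shift table does exist and the rule still has nothing to act on. If the rule is instead taken to govern that table, unscheduled ECGs should enter it, and Section 15.5 does not say how.

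Two stronger readings are tempting but unsupported:
- *That end of treatment is undefined.* Section 15.5 does not define it, but it refers to the protocol for when ECGs are taken. Protocol Table 1 has an End-of-Treatment column with an ECG in it, and Protocol Section 7.2 fixes its timing. A clarifying phrase is enough.
- *That the SAP table drops participants still on treatment at cut-off.* Section 9 does say "For participants with treatment ongoing at cut-off date, all data from the first study intervention up to the cut-off date will be considered" as on-treatment. Those participants lack a scheduled post-baseline ECG because the protocol schedules none during treatment. No SAP table can supply it, and a worst-value column would help only those with an unscheduled ECG. The second analysis, at 15 months, can also pick up participants who have stopped treatment since the first.

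**Conclusion.** The point holds in a limited form. Followed as written, the only ECG table uses 1 of the 2 scheduled post-baseline ECG visits and has no worst on-treatment value through which unscheduled ECGs could enter. Abnormalities at those times appear only in the listing unless they are reported as adverse events.

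This assumes that end of treatment means the End-of-Treatment visit. If it meant the last on-treatment value, some 28-day ECGs would enter, but an abnormality that had resolved by then would still go uncounted.

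The number of abnormalities left uncounted cannot be given. A reader might infer that ECG data are lost or that cardiac safety goes unmonitored; neither follows, given the listing and the adverse-event routes. The effect is confined to a descriptive safety output. The primary endpoint, its test and the sample size are untouched. It is a cheap improvement, not a defect that threatens a conclusion.

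**What to change.** In SAP Section 15.5:
- Keep the planned shift and state that the second value is the one from the protocol's End-of-Treatment visit.
- Add a column for baseline to worst on-treatment ECG interpretation, including unscheduled ECGs and those 28-day ECGs that fall within the on-treatment period.
- State how the eCRF interpretation categories are ordered, so that worst is defined.
- Show the number of participants with at least one post-baseline ECG as the denominator for the new column.
- Label the new column as including unscheduled, possibly symptom-driven ECGs.

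The cost is a few lines of SAP wording and one extra column, using data already collected. The downside is uneven ascertainment: unscheduled ECGs will exist for only some participants, so the proportion in the new column should not be read as an incidence under uniform monitoring. Keeping the End-of-Treatment shift beside it preserves a comparison based on a scheduled visit.

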### **ECOG Performance Status**

The ECOG Performance Status will be derived from the data collected on the “ECOG Performance Status” eCRF page.

The ECOG shift from baseline to the highest score during the on-treatment period will be summarized.

ECOG performance status will also be presented in a listing at each timepoint.

### **Non-protocol Related Hospital Visits**

Participant’s non-protocol related hospital visits will be listed from data collected on the “Non Protocol Related Hospital Visit” eCRF page. The listing will include participant identifier, age, sex, race, total number of pre-planned ambulant (outpatient) hospital visits since the last study

visit, total number of unplanned ambulant (outpatient) hospital visits since the last study visit, total number of nights spent in the hospital for pre-planned overnight (inpatient) hospital visits since the last study visit and total number of nights spent in the hospital for unplanned overnight (inpatient) hospital visits since the last study visit.

## 16 Analyses of Other Endpoints

### 16.1 Pharmacokinetics

The analyses described in this section will be performed by the Clinical PK/PD group (CPK) of Translational Medicine, Merck Healthcare KGaA, Darmstadt, Germany, or by a Contract Research Organization selected by the Sponsor. Pharmacokinetic listings and individual data will be presented based on the Safety Analysis Set. Summaries and statistical analyses will be based on the PK Analysis Set. Only subgroup sample size with a minimal 3 subjects will be displayed.

Pharmacokinetic concentrations/parameters refer to bintrafusp alfa concentrations/PK parameters.

#### 16.1.1 Missing/non-quantifiable PK Data Handling

##### Concentrations below the lower limit of assay quantification

Pharmacokinetic concentrations below the lower limit of quantification (<LLOQ) will be set to zero for calculating parameters and descriptive statistics.

##### Deviations, missing concentrations, and anomalous values

There will be no imputation of missing data. Concentrations will be set to missing in summary tables if the value is reported as no result. Pharmacokinetic concentrations which are erroneous due to a protocol deviation (as defined in the clinical study protocol), documented handling error, or analytical error (as documented in the bioanalytical report) may be excluded from the PK analysis if agreed upon prior to performing a statistical analysis. In this case the rationale for exclusion must be provided in the CSR.

##### Exclusions for concentration data (and $C_{EOI}/C_{trough}$ ) descriptive statistics

- Positive pre-dose values on day 1
- Concentration observed at the end of infusion ( $C_{EOI}$ ) <LLOQ
- In case of missed dose, exclude all concentrations until intended dosing is resumed
- Concentration observed at the end of the dosing interval ( $C_{trough}$ ) values in case samples are taken at least 7 days late or early

Any other PK concentrations that appear implausible to the Pharmacokineticist/PK/Pharmacodynamic Data Analyst must not be excluded from the analysis. Any implausible data will be documented in the relevant listing/table.

If a PK parameter cannot be derived from a participant's concentration data, the parameter will be coded as NC (not calculated). (Note that NC values will not be generated beyond the day that a

participant discontinues the treatment). For statistical analyses, PK parameters coded as NC will be set to missing.

If an individual participant has a known biased estimate of a PK parameter (due for example to a deviation from the assigned dose level), this participant/value will be excluded from the descriptive statistics, and instead the result will be listed in a separate table.

### 16.1.2 Descriptive PK Analysis

#### Presentation of PK Concentration Data

A by-participant listing will present PK sample times, time deviations, and concentrations based on the Safety Analysis Set. Concentrations will be reported with the same precision as the source data.

#### Presentation of PK Parameter Data

The PK parameters listed below will be taken directly from the observed bintrafusp alfa concentration-time data.

$C_{trough}$	The concentration observed immediately before next dosing (corresponding to pre-dose or trough concentration for multiple dosing).
$C_{EOI}$	The concentration observed immediately at the end of infusion.

Individual PK parameters will be listed by nominal study day based on the Safety Analysis Set. Individual PK parameters will be reported with the same precision as the source data.

Pharmacokinetic parameter data will be presented in tables and descriptively summarized by nominal study day using: number of non-missing observations (n), arithmetic mean (Mean), standard deviation (StD), coefficient of variation (CV%), minimum (Min), median (Med), maximum (Max), geometric mean (GeoMean), StD of log-transformed data (logStD), the geometric coefficient of variation (GeoCV%) and the 95% CI for the GeoMean (LCI 95% GM, UCI 95% GM). Summaries will be based on the Pharmacokinetic Analysis Set. Subgroup analysis is done with at least 3 subjects

Additional table(s) will summarize  $C_{trough}$  and  $C_{EOI}$  with further stratification by ADA subsets ever positive and never positive, based on the PKADA. Additional table(s) will summarize  $C_{trough}$  and  $C_{EOI}$  with further sub-stratification by nAb subsets ever positive and never positive, based on the PKNAB. For nAb subsets, summaries will be done for ever positive in either of 2 nAb assays (PDL1 and TGF $\beta$  receptor neutralization; PDL1+/TGF $\beta$ +, PDL1+/TGF $\beta$ -, PDL1-/TGF $\beta$ +) versus never positive (PDL1-/TGF $\beta$ -). Additional table(s) will summarize  $C_{trough}$  and  $C_{EOI}$  with stratification by Japanese, non-Japanese Asian, all Asian and all non-Asian participants based on the PKAS.

Additional table(s) will summarize  $C_{trough}$  and  $C_{EOI}$  with further sub-stratification by ADA subsets ever positive and never positive and, nested within, Japanese, non-Japanese Asian, all Asian and all non-Asian participants based on the PKADA. Additional table(s) will summarize  $C_{trough}$  of ADA ever positive subjects with further sub-stratification by ADA subgroups (e.g. Pre-existing,

Treatment boosted, Treatment emergent, Transient positive, Persistent positive), based on the PKADA. For nAb ever-positive subjects, serum bintrafusp alpha  $C_{trough}$  will be descriptively summarized in additional table(s) for nAb status subgroups (positive in any of 2 nAb assays), based on the PKNAB. Additional table(s) will summarize  $C_{trough}$  of ADA ever-positive subjects with further sub-stratification by ADA subgroups and, nested within, Japanese, non-Japanese Asian, all Asian, and all non-Asian participants, based on the PKADA. For nAb ever-positive subjects, serum bintrafusp alpha  $C_{trough}$  will be descriptively summarized in additional table(s) for nAb status subgroups (positive in any of 2 nAb assays) and, nested within, Japanese, non-Japanese Asian, all Asian, and all non-Asian participants, based on the PKNAB. Additional table(s) will summarize  $C_{trough}$  of ADA Treatment-emergent subjects and nAb Treatment-emergent subjects by PK day relative to seroconversion, for all subjects, Japanese, non-Japanese Asian, all Asian and non-Asian participants based on the PKADA and PKNAB, respectively. Only subgroup sample size with a minimal 3 subjects will be displayed.

Pharmacokinetic parameters will be reported to 3 significant figures. In export datasets, as well as in the SDTM PP domain, PK parameters will be provided with full precision and will not be rounded. Descriptive statistics of PK parameter data will be calculated using full precision values and rounded for reporting purposes only.

The following conventions will be applied when reporting descriptive statistics of PK parameter data:

- Mean, Min, Med, Max, GeoMean, 95% CI: 3 significant digits
- StD, logStD: 4 significant digits
- CV%, GeoCV%: 1 decimal place

Individual PK  $C_{trough}$  and  $C_{EOI}$  values will be plotted versus actual study day on a linear scale, for all participants. Individual data will be presented based on the Safety Analysis Set.

Arithmetic mean ( $\pm SD$ ), GeoMean ( $\pm \log StD$ ), and Med  $C_{trough}$  and  $C_{EOI}$  will be plotted versus nominal study day on a linear scale. Summaries will be based on the Pharmacokinetic Analysis Set.

Additional figure(s) will present Mean, GeoMean, and Med  $C_{trough}$  and  $C_{EOI}$  with further stratification by ADA subsets ever positive and never positive, based on the PKADA, as long as both subsets consist of 3 or more participants. Additional figure(s) will present Mean, GeoMean, and Med  $C_{trough}$  and  $C_{EOI}$  with further sub-stratification by nAb subsets ever positive and never positive, based on the PKNAB, as long as both subsets consist of 3 or more participants. Additional figure(s) will present Mean, GeoMean, and Med  $C_{trough}$  and  $C_{EOI}$  with stratification by Japanese, non-Japanese Asian, all Asian and all non-Asian participants, based on the PKAS. Only subgroup sample size with a minimal 3 subjects will be displayed.

For ADA treatment-emergent subjects with at least one  $C_{trough}$  measurement before and after ADA seroconversion, individual  $C_{trough}$  will be plotted versus PK day relative to seroconversion (for readability, split further into groups of 10 subjects or fewer as needed), for all subjects, Japanese, non-Japanese Asian, all Asian, and all non-Asian participants, based on the SAF. Box plots will

be prepared for  $C_{trough}$  versus PK day relative to seroconversion, for all subjects, Japanese, non-Japanese Asian, all Asian, and all non-Asian participants, based on the PKADA.

For nAb treatment-emergent subjects with at least one  $C_{trough}$  measurement before and after nAb seroconversion (earliest of 2 assays if positive in both), individual  $C_{trough}$  will be plotted versus PK day relative to seroconversion (for readability, split further into groups of 10 subjects or fewer as needed), for all subjects, Japanese, non-Japanese Asian, all Asian, and all non-Asian participants, based on the SAF. Box plots will be prepared for  $C_{trough}$  versus PK day relative to seroconversion, for all subjects, Japanese, non-Japanese Asian, Asian, and non-Asian, based on the PKNAB.

CCI

CCI

